Early clinical experience with favipiravir for COVID-19 is promising. An open-label nonrandomized trial of 80 patients with COVID-19 in China identified a significant reduction in the time to SARS-CoV-2 viral clearance in patients treated with favipiravir compared to historical controls treated with lopinavir/ritonavir. Patients with mild or moderate COVID-19 were enrolled within 7 days from disease onset; those with severe or critical disease, ≥ 75 years old, chronic liver disease, or end-stage renal disease were excluded. Patients in the intervention arm received Favipiravir 1600 mg PO BID on day 1 followed by 600 mg PO BID on days 2-14. Both arms were co-treated with inhaled IFN- $\alpha 1b$ 60 μg BID and therapy was continued until viral clearance, up to a maximum of 14 days. Thirty-five patients were assigned to favipiravir and 45 patients to lopinavir/ritonavir, with a median age of 47 (IQR 35.8-61); 13.7% were ≥ 65 years old. There was a significant reduction in the median time to viral clearance with favipiravir (4 days; IQR 2.5-9) as compared to lopinavir/ritonavir (11 days; IQR 8-13; p <0.001). Further, by day 14, 91.4% of patients in the favipiravir arm had radiographic improvement versus 62.2% of the lopinavir/ritonavir arm. There was a significantly lower rate of adverse events in patients receiving favipiravir (11.4% v. 55.6%, p<0.01).

In an open-label randomized trial in China, 240 patients with confirmed COVID-19 were randomized to favipiravir or arbidol. Favipiravir was given at 1600 mg PO twice on day 1 followed by 600 mg PO BID until day 7-10. The clinical recovery rate by day 7 of treatment was higher amongst patients receiving favipiravir, albeit not achieving statistical significance (61.21% v. 51.67%, p=0.1396). Amongst patients with moderately severe disease, there was a significantly higher rate of clinical recovery by day 7 with favipiravir (71.43% v. 55.86%).

Given the demonstrated in-vitro of activity of favipiravir against SARS-CoV-2 and signals of benefit in early clinical experience for COVID-19, further studies are urgently needed. To address this need, there are several active clinical trials to assess the therapeutic efficacy for COVID-19. However, no trials to date have focused on outbreak control, an area of significant need. It is critical to evaluate the efficacy of favipiravir as chemoprophylaxis against COVID-19 using a placebo-controlled randomized trial.

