Rationale: In contrast to influenza which has an estimated serial interval of 2.2-2.8 days, ⁷³ COVID-19 has been identified to have a serial interval ranging from 4.4-7.5 days, justifying the use of a longer-time span between cases for the purposes of outbreak definition.

Outbreak control

Outbreak control is defined as no new cases of COVID-19 in residents for 24 consecutive days up to day 40 after the start of prophylaxis.

Rationale: The experience with oseltamivir for influenza is such that when it is given for post-exposure prophylaxis, it also has activity for pre-emptive therapy. As a result, oseltamivir

can both prevent incident cases and resolve pre-symptomatic infections, leading to a rapid termination of an outbreak with universal prophylaxis with oseltamivir. Nonetheless, pre-emptive therapy is often incompletely effective, and it is common to see new cases of influenza with onset within the first 2-4 days (one incubation period) of influenza, and occasionally, a single case occurs later.

We do not yet know if any drugs are effective for therapy of COVID-19 or pre-emptive therapy of subclinical COVID-19. It is possible that drugs may be effective for prophylaxis but not pre-emptive therapy. For COVID-19, if the therapy is effective for prophylaxis but ineffective for pre-emptive therapy, new cases may continue to be observed during the first incubation period (median 5 days, 95th percentile of 12.5 days) after prophylaxis is started. If prophylaxis is completely effective, then no cases should occur after this point. However, if individual level prophylaxis is incompletely effective, or if transmission occurs to residents or staff not able to take prophylaxis, then some transmission might occur without compromising outbreak control. Assuming that the period of infectivity is 10 days, and the maximum incubation period is 14 days, then an outbreak can be considered controlled (or ended) if no cases occur for 25 days after the day of onset in the last case.

Study Day 1

Day 1 is defined as the first day of receipt of chemoprophylaxis in the LTCH.

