6.4 Endpoint Assessment

The primary outcome (primary endpoint) will be control of outbreak, defined as no new cases of COVID-19 in residents for 24 consecutive days up to day 40 after the start of prophylaxis. This outcome is dichotomous (yes/no) and will be determined at the level of the cluster (LTCH unit).

Secondary outcome measures (endpoints) are:

- 1. The proportion of residents of included LTCH units who die up to day 40, and up to day 60
- 2. The proportion of residents of included LTCH units who were uninfected at baseline and develop new symptomatic microbiologically confirmed COVID-19 up to day 40
- 3. The proportion of exposed staff uninfected at baseline in whom SARS-CoV-2 infection is identified up to day 14 and up to day 40
- 4. The proportion of residents of included LTCH units hospitalized up to day 40
- 5. The proportion of residents of included LTCH units who discontinue study medication due to adverse events
- 6. The proportion of LTCH staff of included LTCH units who discontinue study medication due to adverse events.
- 7. The occurrence of new microbiologically confirmed COVID-19 infections in residents in other units of the facility up to day 40 (dichotomous, at LTCH level)
- 8. The proportion of previously unaffected LTCH units of the remainder of the facility in which a case of COVID-19 is identified
- 9. The proportion of residents in the remainder of the facility who develop COVID-19 infections up to day 40

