13.2 Screening, consenting and initial data collection Visit

The purpose is to rapidly assess participant eligibility and obtain written informed or preliminary verbal consent to participate in the trial, as eligibility and consent are required from at least 80% of residents on the outbreak ward in order to randomize. A nasopharyngeal or nasal swab will be obtained from all residents on day 0, and from all staff as soon as practical.

The study coordinator will:

- Review the patient's chart and medication record to assess eligibility; if possible, this will be performed remotely either via research staff having access to electronic charts, or by having a staff member in the home transmit the information by telephone or fax.
- If written informed consent has not yet been obtained, provide and review the informed consent document via email / fax / telephone / video link with each resident, substitute decision maker or staff person, and obtain and document verbal consent to participate.
- Advise the participant/substitute decision maker that written consent will be required as soon as possible and agree on the method by which this will be done.
- Provide contact information for the study, such that each participant has access to study personnel at any time to answer questions
- Obtain multiple forms of contact information for consenting participants, including multiple telephone numbers, an email address, and a mailing address for study material delivery.
- For study staff:
 - o Complete the baseline interview for study staff.
 - o Decide whether staff will complete daily diaries online or on paper
 - Review with the participant how to access and complete the symptom/adherence diary and questionnaires, and encourage immediate completion of the baseline questionnaire on the day of the visit.

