13.3 Medical Oversight

Confirmation of eligibility, assessment of adherence of study drug/placebo, evaluation of overall participant safety, review/assessment of minor and/or serious adverse events (including classification of adverse events according to seriousness, severity, relatedness and expectedness), and final sign off of data collection will be done by the qualified investigator/principal investigator ([name]) or a medically qualified and licensed delegated physician.

Table 1. Schedule of Events for Residents

Visit	Screening (Day 0)	Baseline (Day 1)	Day 14±2d	Day 40±4d	Day 60±7d
Visit format	Remote	Remote	In person	In person	Remote or
					in person
Eligibility	X				
assessment					
Informed consent	X				
Cluster		X			
randomization					
Dispensing study		X			
drugs					
Assessment for		Daily, by LT	ΓC staff (fax to	study)	
COVID-19		Chart review by	study staff, da	ay 14 & 40	
Concomitant medi-	X		X	X	
cation assessment					
Adverse event		Daily by LT	C staff (fax to	study)	SAE only
assessment		Chart review by study staff, day 14 & 40			
Death/hospital		Daily by LTC staff (fax to study)			X
transfer document.		Chart review by study staff, day 14 & 40			
Nasopharyngeal/	X		X	X	
nasal swab					
Medication			X	X	
adherence					

Table 2. Schedule of Events for Staff

Visit	Screening (Day 0)	Baseline (Day 1)	Day 14±2d	Day 40±4d		
Visit format	Remote or	Remote	Remote or in person	In person		
	in person*					
Eligibility	X					
assessment						
Informed consent	X					
Cluster		X				
randomization						
Dispensing study		X				
drugs						
Interview by study	X		X	X		
staff						
Concomitant medi-	X		X	X		
cation assessment						
Adverse event			X	X		
assessment						
Daily diary		Daily symptom/adverse event/adherence diary to be completed				
Visit-specific	X		X	X		
questionnaire						
Nasopharyngeal/	X^1		X	X		
nasal swab						
Pill count				X		

^{*}If staff are willing and able to do their own nasal swab, then visits will be remote. Consents and questionnaires will be returned by mail or fax, or collected at the LTCH. Pill bottles will be returned to a secure location at each LTCH to be collected by study staff.

¹For staff, nasopharyngeal/nasal swabs may be obtained on day 0-3, as they may not be obtained until the first time that the staff member attends at the LTCH to complete a shift. New staff starting work during the outbreak will be requested to have a swab on the first day that they work.

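### The staff baseline swab may be taken after a staff member's first dose, so the at-risk group for the staff infection outcome may depend on arm

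*Protocol*

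**What the plan says.** Protocol section 6.4 defines secondary outcome 3 as "The proportion of exposed staff uninfected at baseline in whom SARS-CoV-2 infection is identified up to day 14 and up to day 40".

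The timing of the staff baseline swab is described in four places:

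- Section 6.1 has consenting residents and staff screened on day 0, day 14 and day 40.
- Section 12.2.1 equates baseline with day 0 for all participants.
- Section 13.2 separates the two groups: "A nasopharyngeal or nasal swab will be obtained from all residents on day 0, and from all staff as soon as practical".
- Table 2 in section 13.3 (Medical Oversight) marks the staff swab under Screening (Day 0). Footnote 1 widens this to "nasopharyngeal/nasal swabs may be obtained on day 0-3", because "they may not be obtained until the first time that the staff member attends at the LTCH to complete a shift". It adds: "New staff starting work during the outbreak will be requested to have a swab on the first day that they work".

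Table 2 puts cluster randomization and dispensing on day 1. Section 5 fixes that day for the home, not for the person: "Day 1 is defined as the first day of receipt of chemoprophylaxis in the LTCH". Sections 10.1.5 and 13.3 (Baseline Visit) have research coordinators arrange transport of staff drug to the participants, with no condition that a swab be taken first.

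**The concern.** A baseline status that defines an at-risk group should be measured before treatment can influence it. Residents meet that condition, since they are swabbed on day 0. Staff need not. A staff member may receive drug on day 1, start it, and be swabbed at a first shift on day 2 or 3.

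For such a person, two things can make membership of the denominator depend on arm. The drug may change whether an existing infection is detectable. It may also change whether an infection is acquired between the first dose and the swab. Analysing by intention to treat (section 15.3.2) does not repair this, because the selection happens before the analysis starts.

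The protocol also does not say whether a first positive on days 1 to 3 is a baseline infection or an outcome event. A statistical analysis plan, not available here, could settle that rule. It could not recover a pre-dose swab that was never taken.

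**Working it through.** **Order of events.** Three facts from the protocol together allow the problem:

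1. The swab window runs from day 0 to day 3.
2. Dispensing is on day 1.
3. No passage ties the swab to the individual's first dose.

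So a swab before dosing and a swab after dosing both comply with the protocol. For new staff the order is equally open: their swab is requested on the first working day, and no passage dates their first dose relative to it.

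**Could drug matter within the window?** Section 4.2 reports: "There was a significant reduction in the median time to viral clearance with favipiravir (4 days; IQR 2.5-9"; the comparator's median is 11 days. The lower quartile of 2.5 days is close to the longest interval between a day 1 dose and a day 3 swab. An effect is plausible but not established.

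**Possible size.** The protocol gives no figure for this point, so the following is illustration. All inputs are assumptions:

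- q, infected at day 0: 5% or 10%
- r, infected on days 1 to 3: 2% or 4%
- s, infected later: 10% or 20%
- L, share swabbed on day 3: 25% to 100%; the rest are swabbed on day 0
- Swab sensitivity 0.9, except Se = 0.6 on day 3 under favipiravir
- d, chance that a missed baseline infection is found later: 0.5
- A positive day 3 swab removes the person from the denominator

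Formulas, per person enrolled:

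- Day 0 swab: denominator 1 − 0.9q; events 0.1·q·d + r + s
- Day 3 swab: denominator 1 − Se(q + r); events (1 − Se)·q·d + (1 − Se)·r + s
- Risk: events divided by denominator, each averaged with weights 1 − L and L

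Worked case with q = 0.10, r = 0.04, s = 0.10, L = 1 and no drug effect on acquisition:

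- Placebo: (0.005 + 0.004 + 0.10) / (1 − 0.126) = 0.109 / 0.874 = 12.5%
- Favipiravir: (0.020 + 0.016 + 0.10) / (1 − 0.084) = 0.136 / 0.916 = 14.8%
- Observed risk ratio: 1.19, where the truth is 1.00

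Observed risk ratio when the truth is 1.00:

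| L | q 5%, r 2%, s 10% | q 10%, r 4%, s 10% | q 10%, r 4%, s 20% |
|---|---|---|---|
| 25% | 1.02 | 1.04 | 1.02 |
| 50% | 1.05 | 1.08 | 1.04 |
| 75% | 1.07 | 1.13 | 1.06 |
| 100% | 1.10 | 1.19 | 1.08 |

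**Direction.** Set q = 0.10, r = 0, s = 0.10, L = 1 and let missed infections never be found (d = 0). The ratio is (0.10/0.94) / (0.10/0.91) = 0.97. With the same q, r, s and L, it equals 1 when 0.91(0.04d + 0.10) = 0.94(0.01d + 0.10), which gives d = 0.003/0.027 = 0.11. Below that the bias favours favipiravir; above it, placebo.

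**Early events.** Suppose instead that the drug halves acquisition from day 1 and leaves sensitivity at 0.9. The ratio is then 0.50 to 0.52, against 0.51 to 0.52 with every swab on day 0. The ratio barely moves, but events are lost: with q = 10%, r = 4%, s = 10%, placebo risk falls from 15.9% with all swabs on day 0 to 12.5% with all on day 3.

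**Primary outcome.** Exact enumeration for 8 versus 8 units at 12.5% and 87.5% with the two-sided Fisher test gives power 0.870, in line with the >85% in section 15.2. That outcome is based on residents at unit level and does not use staff swabs.

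**The case against.** The window is a stated feasibility choice: some staff are not on site until their first shift, and section 13.1 asks that contacts be virtual wherever possible. Staff drug travels separately, so some staff may be swabbed before dosing even on day 2 or 3. One secondary outcome of nine is touched, in staff only. All of this stands and limits the weight of the point, but the order of swab and dose is still left uncontrolled.

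A reader might infer four stronger things that the protocol does not support:

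- **That staff baseline is measured on treatment.** Day 1 is defined for the home, and no passage dates an individual's first dose. It may be on treatment.
- **That positives on days 1 to 3 are recorded as baseline.** The protocol does not state this.
- **That the bias favours favipiravir.** Staff are swabbed again on day 14 and day 40, and symptomatic staff are tested (section 12.2.1). Missed infections can therefore resurface as events, which pushes the other way.
- **That the clearance times in section 4.2 give the size.** An exponential curve through the medians of 4 and 11 days gives 29% to 41% cleared at 2 to 3 days on favipiravir, against 12% to 17% on the comparator. That curve does not fit the reported quartiles. It predicts 1 − 2^(−2.5/4) = 35% cleared at 2.5 days and 1 − 2^(−8/11) = 40% at 8 days, where the quartiles say 25% each. The study was also non-randomized, enrolled diagnosed patients, and compared favipiravir with lopinavir/ritonavir, not placebo.

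**Conclusion.** The point holds as a gap in sequencing. Footnote 1 permits a staff baseline swab after the individual's first dose, so the denominator of secondary outcome 3 may be selected on a measurement affected by arm. The footnote also conflicts with the day 0 wording in sections 6.1 and 12.2.1.

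The size is unknown and probably modest. The range of 0.97 to 1.19 around a true ratio of 1.00 rests wholly on the assumed prevalence, sensitivity, share of late swabs and chance of later detection. Its upper end needs every swab on day 3 and a marked early drug effect on PCR. The sign cannot be fixed in advance, so a reader of the results could not correct for it.

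The primary outcome, its power and the resident outcomes are unaffected. This is an inexpensive improvement worth making, not a flaw that threatens the trial's main conclusion.

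**What to change.** 1. Amend footnote 1 so that the staff swab, including that of new staff, is taken before the person's first dose. Where the person is not on shift, coordinators deliver a self-collection nasal kit with the study drug. Drug is neither withheld nor delayed if a swab cannot be obtained.
2. Record the time of the swab relative to the first dose for every staff participant.
3. Reconcile footnote 1 with sections 6.1, 12.2.1 and 13.2.
4. For outcome 3, define baseline by pre-dose swabs only. Class first positives after dose 1, and staff without a pre-dose swab, by one rule that is identical in both arms.
5. Add a sensitivity analysis in all exposed staff regardless of baseline swab.

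The procedures already exist. The Table 2 asterisk note allows self-swabbing ("If staff are willing and able to do their own nasal swab, then visits will be remote"), section 13.4 has staff at home on day 14 swab themselves and bring the specimen to their next shift, and coordinators already arrange delivery of staff drug. The number of swabs is unchanged. The costs are a wording amendment, a kit in the drug package, more self-collected nasal and fewer nasopharyngeal specimens at baseline, and some staff who will still lack a pre-dose swab.

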13.3 Baseline Visit (Day 1)

• Dispense study drug:

- Medications are provided to LTCH residents in Ontario by third-party pharmacies. The pharmacies for participating LTC facilities will be approached in advance to coordinate mechanisms for timely distribution of trial drugs. Medications will be distributed from the central research pharmacy to the regional dispensing pharmacy for distribution to the LTCH. All medications will be dispensed and administered by long-term care facility nursing staff as part of routine medication administration.
- o For staff, the medication will be dispensed from the research pharmacy to study research coordinators who will be responsible for arranging transportation to the study participants and documenting this process.

13.4 Data collection Day 2 to Day 40

Efforts will continue to ensure that either an electronic or hard copy of the signed written informed consent form is obtained from each participant or their substitute decision maker. This should be obtained as soon as possible, ideally by day 2.

From day 0 until the outbreak is declared over, the LTCH will fax daily line lists of the outbreak to the study (these will already be being routinely sent to the local public health unit). These lists record all residents and staff who meet the case definition, who are tested for COVID-19, as well as the results of any testing. For this study, we will add to the line list a record of any potential adverse events, and discontinuation of study drug. Study staff will also report any deaths or transfers to hospitals during the outbreak. In addition, the study coordinator responsible for the particular outbreak will participate in all virtual outbreak meetings between public health units and the LTCH, to ensure that no information is missed.

On day 14, a study staff member will visit the home and review charts (remote chart review will occur if possible), to ensure concordance between chart review and records on the line list and testing of residents meeting the case definition. Validation of records of deaths, transfer to hospital, adverse events, and medication compliance will also occur. At this visit, all consenting residents who have not had a nasopharyngeal swab obtained within the last 48 hours will have nasopharyngeal swabs obtained (these may be obtained either by study staff or LTCH staff); participating staff who are working that day will also have an NP swab obtained. Participating staff who are at home on day 14 will obtain a nasal or mid-turbinate swab at home and bring it to the LTCH for testing at the time of their next shift.

The study staff member will also identify the number of residents and staff on other units of the home who have been diagnosed with COVID-19

The day 14 LTCH visit will be by a single staff person who will visit the LTCH, appropriate PPE supplied by the study will be used, and all procedures established by the LTCH and their local public health unit will be followed.

At day 14, all participating staff will be contacted by telephone to check on and encourage daily diary completion and to complete a questionnaire regarding symptoms, potential adverse events and medication adherence.

13.5 Day 40 Visit

For residents, study activities include:

- Chart review (remote chart review will occur if possible), to ensure concordance between chart review and records on the line list and testing of residents meeting the case definition.
- Validation of records of deaths, transfer to hospital, adverse events
- Review of medication compliance.
- Nasopharyngeal swabs from all consenting residents who have not had a nasopharyngeal swab obtained within the last 48 hours
- Documentation of the number of COVID-19 cases which have been identified in non-consenting residents on the outbreak units, and in residents on other units in the facility (no information will be collected about these cases).

For staff, study activities include:

- Interview and questionnaire regarding symptoms, concomitant medications, adverse events, and medication adherence
- Nasopharyngeal/nasal swab from those who have not had a nasopharyngeal/nasal swab obtained within the previous 48 hours
- Review of pill count, and arrangements for return of remaining pills and daily diaries if this has not already happened.
- Documentation of COVID-19 cases which have been identified in staff working on other units in the facility

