9. ALLOCATION AND BLINDING PROCEDURES

9.1 Allocation

Each nursing home unit will only be randomized once all members of the unit or their substitute decision makers (SDMs) give preliminary consent, decline or are classified as not contactable; at least 80% of residents or their SDMs within the unit must give consent to take the study medication (favipiravir or placebo) for unit eligibility for randomization. Every effort will be made to contact residents and/or their substitute decision makers within 48 hours. Those who cannot be contacted within 96 hours will not be eligible to receive study drug. LTCH staff may be enrolled on a continuing basis, recognizing that new LTCH staff may be needed to start work on the unit during the outbreak.

As LTCH units will be enrolled prospectively, we will use probabilistic minimization on the baseline COVID-19 attack rate on the unit to allocate units 1:1 (8 intervention units, 8 control units) to the 2 groups. Probabilistic minimization will be performed by an independent statistician at the Applied Health Research Centre (AHRC) at St. Michael's Hospital using the R package *minirand* (R Foundation for Statistical Computing, Vienna, Austria). Consent of LTCH staff and residents prior to randomization of the cluster, and use of placebo as a control intervention will help minimize the risk of "empty" clusters or the use of interventions that are not part of this protocol.

Each person for whom written informed or preliminary verbal consent was obtained will be entered in the electronic case report form (eCRF) so that an adequate number of uniquely coded study drug bottles/blister packes for all consenting members of the LTCH unit can be prepared. An automated audit trail will record the time, date, allocation, and participant identification numbers. Those who withdraw preliminary consent or decline study drug will be asked to consent to be followed-up for primary and secondary outcome. Those who also decline follow-up will be excluded from intention-to-treat analyses. Waiver of consent will be requested of participating sites to record the number of non-participating residents and LTCH staff, and the number and date of onset of cases of symptomatic microbiologically confirmed COVID-19 in these two groups.

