9.2 Blinding

The trial will be blinded with the use of placebo controls. Favipiravir will have a placebo which is similar in size and shape, but can be distinguished because of color differences and an imprint on the surface of favipiravir tablets which could not be matched for the placebo given the timelines of this trial. However, favipiravir and placebo will be packaged in blister packages of identical appearance.

Drug supply will be dispensed by external pharmacies, which supply multiple LTCHs, therefore we will not be able to completely rule out that pharmacists dispensing medication will remain blinded. In addition, both placebo and favipiravir can be crushed before administration, which is necessary for some residents, and will not be identical in appearance when crushed. However, since favipiravir is not otherwise available in Canada, residents of included LTCHs will only receive one type of intervention (either drug or placebo, depending on the allocation of the LTCH unit), and no information will be provided by external pharmacies, research personnel or investigators to the LTCHs about, color, imprinting, appearance after crushing, and about the allocated intervention. Therefore, it is unlikely that LTCH staff and residents will be unblinded.

All study investigators will be blinded, except for an independent statistician from AHRC who will be responsible for probabilistic minimization, but will otherwise not be involved in the conduct of the trial. Outcome assessors, who will extract outcome data from the LTCHs' administrative data, will be blind to treatment allocation. The statistician conducting the analysis will also be unaware of treatment allocation.

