10.1.4 Storage and Stability

Favipiravir is a novel nucleic acid (pyrazine molecule) analogue that interferes with viral ribonucleic acid (RNA) replication. Favipiravir is supplied as a light yellow, film-coated tablet for oral administration containing 200 mg favipiravir. Favipiravir tablets are to be kept in a dry area, stored at 15° C to 30° C and shielded from direct light.

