10.1.5 Study Drug Dispensation

For residents, study drug will be provided from a research pharmacy to the dispensing pharmacy for each enrolled LTCH. The dispensing pharmacy will be responsible for packaging and arranging transportation of medications to each LTCH. The medications will then be dispensed to each enrolled resident by the LTCH nursing staff as per routine medication administration processes.

For LTCH staff, the medication will be dispensed from the research pharmacy to research coordinators who will be responsible for arranging transportation to the study participants and documenting this process.

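### The blind promised in Section 9.2 is unprotected for study personnel who take back and count distinguishable staff tablets and also collect adverse events and check outcomes

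*Protocol*

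**What the plan says.** **The promise.** Section 9.2 states: "All study investigators will be blinded, except for an independent statistician from AHRC". It adds that outcome assessors, described as working from the homes' administrative data, and the analysing statistician are also unaware of allocation. Section 6.1 calls the trial partially blinded.

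**The concession.** The same section says the placebo "can be distinguished because of color differences and an imprint on the surface of favipiravir tablets". The safeguards offered are that "favipiravir and placebo will be packaged in blister packages of identical appearance", that a home only ever receives one product, and that nobody tells the home what either product looks like. A possible leak is admitted only for dispensing pharmacists.

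**The handling of the staff supply.**
- Section 10.1.5, repeated under the Baseline Visit in 13.3: "the medication will be dispensed from the research pharmacy to research coordinators", who arrange its transport to participants.
- Section 9.1 refers to "uniquely coded study drug bottles/blister packes".
- Footnote to Table 2 (Schedule of Events for Staff): "Pill bottles will be returned to a secure location at each LTCH to be collected by study staff".
- Table 2 schedules a pill count at day 40, and the staff list in 13.5 contains "Review of pill count, and arrangements for return of remaining pills and daily diaries if this has not already happened".

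**The concern.** The argument in 9.2 works for people inside a home, who see one product and have no reference. It does not work for people on the study side. They can look up the active tablet in the protocol, and they are the ones who take the tablets back. If the person who sees the tablets also interviews staff about adverse events, reviews charts or helps judge causality, those judgements may be made with knowledge of the arm.

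A whole unit shares one allocation, so a single staff member's leftover tablets disclose the arm of every resident and staff member on that unit. What is at stake is first the adverse-event data and secondary outcomes 5 and 6 (discontinuation for adverse events), and then the checking of deaths and hospital transfers at day 40.

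**Working it through.** The plan gives no figure on this point to reproduce. The check sets the sections side by side.

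**1. Can a tablet reveal the arm without comparing products?** Yes, for anyone who has read the protocol. Section 10.1.4: "Favipiravir is supplied as a light yellow, film-coated tablet for oral administration containing 200 mg favipiravir". Table 1 in 10.1.3 adds that it is round and 8.7 mm across. Section 9.2 says colour and imprint differ from placebo. That study personnel know the protocol is an assumption, but 17.2.2 lists protocol training records among the documents to be monitored.

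**2. Does the reasoning in 9.2 reach study personnel?** No. Each of its elements concerns what a home sees or is told. It also lists research personnel and investigators among those who must not describe the tablets to homes, which treats them as people who may have that information.

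**3. Where are tablets exposed to study personnel?**
- *Going out:* coordinators arrange transport of packs that look alike from outside. Whether the packs hide their contents is not stated.
- *Coming back:* study staff collect bottles. The footnote saying so is attached to staff who swab themselves and have remote visits.
- *Being counted:* day 40. An identical outer pack does not help once tablets are counted. The person counting is not named.
- *Earlier:* 13.7 asks for the day 40 activities when a participant withdraws before day 40, so the count can come forward.

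**4. What else do the same groups do?**
- The study coordinator assesses eligibility and obtains consent (13.2), and the coordinator for a given outbreak attends its outbreak meetings (13.4).
- Study staff review charts and check recorded deaths, transfers and adverse events at day 14 (13.4). The same checks recur in the day 40 list (13.5).
- The day 40 staff list (13.5) puts the symptom and adverse-event interview next to the pill-count review.
- The qualified investigator or a delegated physician assesses adherence, classifies adverse events including relatedness, and signs off the data (13.3, Medical Oversight).

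No section separates drug return and counting from these tasks.

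**5. When does the exposure occur?** Study drug runs to day 25 and the count is at day 40 ± 4, that is day 36 to 44. The ordinary count therefore falls about 40 − 25 = 15 days after dosing ends and at the close of the primary outcome window. Returns soon after day 25 are possible.

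**6. Could it reveal the next allocation?** Enrolment runs from May 10 to October 31, which is 174 days. If 16 units arrive evenly, the spacing is 174 / 16 = 10.9 days. A count at day 40 comes after about 40 / 10.9 = 3.7 further units, and a return at day 25 after about 25 / 10.9 = 2.3. Knowledge gained this way lags recruitment by roughly two to four units.

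**The case against.** The best case against is that the text promises less than it seems to, and that tablets are seen late. Coordinators are called neither investigators nor outcome assessors, the trial is labelled partially blinded, packs look alike from outside, and the count is at day 40. These limits stand. They do not remove the gap: the partial label does not withdraw the specific promises in 9.2, and 13.4 and 13.5 provide for checking, during study visits, the outcomes that 9.2 says blinded assessors extract.

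Several stronger readings are tempting but not supported:

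- *That the blind cannot hold.* The text shows a missing safeguard, not certain unblinding.
- *That the same coordinators handle both arms.* This is plausible with 16 homes, but 13.4 speaks of one coordinator per outbreak and nothing states overlap. The point does not need it, because the active tablet is described in the protocol.
- *That knowing the arm could sway whether a unit reaches 80% consent.* Under 9.1, consent is settled before an independent statistician allocates the unit, so that unit's arm does not yet exist.
- *That the primary endpoint is materially biased.* It counts microbiologically confirmed cases in residents. Section 12.2.1 expects every resident meeting the case definition to be tested, with the study laboratory as back-up, plus swabs at days 0, 14 and 40 and after deaths in the home. A count at day 40 cannot change earlier testing. Symptom-triggered testing between swabs leaves some room if tablets are seen earlier.
- *That a fragile p-value measures the harm.* With 16 units any reclassified unit matters, whatever its cause. This is not an estimate of bias from pill counting.
- *That later allocations become predictable.* The lag shown in the working limits this. Section 9.1 minimises on baseline attack rate and gives no allocation probability, so no guessing rate can be derived.

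**Conclusion.** The point holds in a limited form. Section 9.2 promises blinded investigators and outcome assessors, and its justification stops at the door of the home. Study personnel who can recognise the active tablet take back the staff supply, and the count is reviewed in the same visit (or early-termination visit) as adverse-event interviews and outcome checks. For these people the blind is unprotected.

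The size cannot be stated as a number from the documents. In order of weight:
- The main exposure is adverse-event elicitation and causality, whether a discontinuation is recorded as due to an adverse event, and validation of deaths, transfers and adverse events late in each unit's follow-up.
- The secondary and unquantified exposure is symptom-triggered testing if tablets are seen early, consent of new staff who join after allocation, and guesses about later units.

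This rests on two assumptions: that study personnel know the protocol's tablet description, and that the unnamed person who counts belongs to the group that collects or checks outcomes. The sections on blinding, dispensing, the staff schedule and the day 40 visit should be reconciled. It is a cheap improvement worth making, not a flaw that undermines the trial.

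**What to change.** - **10.1.5:** add the return route. Home staff seal their unused drug and it goes back to the research pharmacy, which already dispenses it. The pharmacy does the count and enters it in a database field closed to blinded personnel until database lock.
- **Table 2 and its footnote:** assign the pill count to the research pharmacy. Study staff may still collect containers, but only sealed ones.
- **13.5 (and so 13.7):** remove pill-count review from the staff visit. The diary, interview and questionnaire already cover adherence there.
- **9.2:** state that anyone who consents participants, interviews staff, reviews charts or assesses adverse events must not view or count study tablets.

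The cost is amendment wording, sealable return packaging and a modest task for an existing pharmacy. The downside is that discrepancies between the count and reported adherence cannot be queried at the interview. Until lock, the investigator's adherence assessment under 13.3 would rest on diary, interview and questionnaire for home staff.
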